### 6.2.2. Primary Effectiveness Endpoint

The primary outcome measure for effectiveness in the MIMICS-2 Study is primary stent patency rate at 12 months.

Patency is defined as no significant reduction in luminal diameter (i.e., < 50% diameter stenosis) since the index procedure. Luminal diameter is the value determined by the independent core lab. Loss of primary stent patency is deemed when PSVR >2.0, or where angiography reveals >50% diameter stenosis, or where the subject undergoes CDTLR. When both imaging modalities are available, angiography takes precedence.

[REDACTED]

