### 6.2.3. Secondary Endpoints

1. Contribution of individual MAE rates for death, major amputation performed on the target limb and CDTLR to the overall MAE rate at 30 days.
2. Long-term safety assessment – overall MAE rate at Month 12 and contribution of individual event rates to the overall MAE.
3. Overall rate and incidence of type of serious adverse events from Day 0 through completion of Study follow-up at Month 36.
4. Technical success reported by the core lab as the percentage of treated lesions in which a final result of ≤50% residual diameter stenosis (in-stent) was achieved at index procedure.
5. Primary stent patency rate: determined at Months 12 and 24 using values of: PSVR >2.0; >2.4; >2.5; and >3.5, each to indicate loss of patency on duplex ultrasound or where angiography reveals >50% diameter stenosis or where the subject undergoes CDTLR. When both imaging modalities are available, angiography takes precedence.
6. Clinical outcome: comparison of Rutherford Clinical Category measured at Baseline, Day 30, Months 12 and 24. Worsening of Rutherford Clinical Category is defined as an increase by one or more categories compared to Baseline or unexpected major amputation of the target limb.

[REDACTED]

[REDACTED]

7. Clinical outcome: comparison of Six-Minute Walk Test measured at Baseline, Day 30, Months 12 and 24 (sub-group of investigational sites).
8. Functional outcome: comparison of the ankle brachial index (ABI) measurement at Baseline, within 30 days after index procedure, then at Months 12 and 24.
9. Functional outcome: comparison of the Walking Impairment Questionnaire at Baseline, within 30 days after index procedure, then at Months 12 and 24.
10. Stent integrity measured as freedom from stent fracture, defined as clear interruption of a stent strut observed in a minimum of two projections, determined by core lab examination of X-rays taken with the leg in extension at 12, 24 and 36 Months.

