#### 9.4.2. Primary effectiveness endpoint:

The primary outcome measure for effectiveness is primary stent patency rate at 12 months as defined in Section 6.2.2. The one-sided lower 97.5% Agresti-Coull confidence bound will be computed for patency and this lower bound will be compared to the effectiveness performance goal of 66% for bare Nitinol stenting as defined by the VIVA Physicians, Inc.[4]. The performance goal will be met if the lower bound is greater than 66%. The mITT analysis population will be used for this endpoint; however, only subjects with valid endpoint data without imputation will be included. This includes all subjects with imaging data qualifying as a 12 month visit and/or subjects without imaging data who experienced a CDTLR through 12 months (365 days). Additionally, if a subject is missing stent patency status at the 12 month visit window but is found to be patent at a later out-of-window date, the subject will be considered patent at 12 months. Sensitivity analyses for excluding missing data will be conducted as described in Section 9.2.3 above.

Both primary endpoints must be met in order to declare trial success.

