## 9.5. Secondary Endpoint Analyses

All secondary endpoints as described in Section 6.2.3 will be tabulated. Means, standard deviations and sample size will be used to summarize continuous characteristics. Distributions of continuous data will be examined and if non-normality is exhibited, medians and interquartile ranges will be presented. Percentages, raw number of subjects exhibiting a characteristic, and sample size will be used to summarize categorical characteristics. Measures collected serially over time (for example, ABI) will be presented at each time point, and the measure at each time point will be compared to the baseline measure as well as tested for trends. All available data will be used for each endpoint and no imputations will be done. The mITT analysis set will be used for these analyses.

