### 9.5.1. Secondary Endpoints

The following endpoints will be summarized as noted above:

- Contribution of individual MAE rates for death, major amputation performed on the target limb and CDTLR to the overall MAE rate at 30 days.
- Long-term safety assessment – overall MAE rate at Month 12 and contribution of individual event rates to the overall MAE. Freedom from MAE will be additionally displayed via Kaplan-Meier plots.

- Overall rate and incidence of type of serious adverse events from Day 0 through completion of Study follow-up at Month 36.
- Technical success reported by the core lab as the percentage of treated lesions in which a final result of  $\leq 50\%$  residual diameter stenosis (in-stent) was achieved at index procedure.
- Primary stent patency rate: determined at Months 12 and 24 using values of: PSVR  $>2.0$ ;  $>2.4$ ;  $>2.5$ ; and  $>3.5$ , each to indicate loss of patency on duplex ultrasound or where angiography reveals  $>50\%$  diameter stenosis or where the subject undergoes CDTLR. When both imaging modalities are available, angiography takes precedence. ■
- Clinical outcome: comparison of Rutherford Clinical Category measured at Baseline, Day 30, Months 12 and 24. Worsening of Rutherford Clinical Category is defined as an increase by one or more categories compared to Baseline or unexpected major amputation of the target limb.
- Clinical outcome: comparison of Six-Minute Walk Test measured at Baseline, Day 30, Months 12 and 24 (sub-group of investigational sites).
- Functional outcome: comparison of the ankle brachial index (ABI) measurement at Baseline, within 30 days after index procedure, then at Months 12 and 24.
- Stent integrity measured as freedom from stent fracture, defined as clear interruption of a stent strut observed in a minimum of two projections, determined by core lab examination of X-rays taken with the leg in extension at 12, 24 and 36 Months.

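### The 12-month primary patency rule has no place for a loss of patency documented before the visit window without CDTLR, so a known failure can be dropped or counted as patent

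*SAP*

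**What the plan says.** **Definition.** SAP 6.2.2 defines patency as "no significant reduction in luminal diameter (i.e., < 50% diameter stenosis) since the index procedure". The success criterion for effectiveness in SAP 9.1 concerns the proportion of subjects whose treated segment stays patent up to 12 months. Both are most naturally read as cumulative.

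**12-month analysis set.** SAP 9.4.2 uses mITT subjects with valid endpoint data and no imputation. It names two groups: "all subjects with imaging data qualifying as a 12 month visit", and "subjects without imaging data who experienced a CDTLR through 12 months (365 days" (the parenthesis closes there). It then adds that a subject without patency status in the window whose stent is patent on a later image counts as patent at 12 months. That addition sets no condition on earlier images. SAP 9.2.8 puts the window at 365 ± 30 days and treats subjects with no data beyond its lower boundary as missing.

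**Later time points.** Secondary patency is "determined at Months 12 and 24 using values of: PSVR >2.0; >2.4; >2.5; and >3.5, each to indicate loss of patency" (SAP 6.2.3). Fracture is "determined by core lab examination of X-rays taken with the leg in extension at 12, 24 and 36 Months". The handling rule in SAP 9.5 is "All available data will be used for each endpoint and no imputations will be done". No denominator or carry-forward rule is given for either endpoint.

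**The concern.** Under a cumulative definition, a stent that has lost primary patency cannot regain it. SAP 9.4.2 applies this to CDTLR, which counts as a failure even without a 12-month image, but not to a loss seen only on an image.

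Take a subject whose core-lab image at Month 8 shows occlusion, who has no CDTLR and who misses the Month 12 image. No route in 9.4.2 admits this subject as a failure, so the subject is left out. If an image after the window then reads below the PSVR cut-off, the same subject enters as a success. Both outcomes favour the device, in the endpoint that is tested against the performance goal.

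SAP 9.4.1 handles the parallel safety case differently: any MAE up to day 30 keeps the subject in the analysis, whatever the later follow-up.

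For Month 24 patency and for fracture at Months 24 and 36 the issue is a silence. A programmer could apply a cumulative rule or a per-visit rule, and a per-visit rule could let a later rate look better than an earlier one.

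**Working it through.** **1. Inputs (SAP 9.1 and 9.4.2).** Goal 66%; one-sided 97.5% Agresti-Coull lower limit; assumed patency 75%; 230 evaluable subjects; 85% power.

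**2. Formula.** With z = 1.96, n' = n + z² = n + 3.84 and p' = (x + z²/2)/n', the lower limit is L = p' − z·√(p'(1 − p')/n').

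**3. The plan's own figure.**
- At n = 230, 165 patent gives L = 65.59% (fail).
- 166 patent gives n' = 233.84, p' = 0.7181, standard error 0.02942, and L = 0.7181 − 1.96 × 0.02942 = 66.04% (pass).
- The pass mark is therefore 166/230 (72.2%). Exact binomial power at 75% is 85.6%, and exact type I error at 66% is 2.7%. The stated sample size of 230 reproduces, and this point does not alter it.

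**4. One subject at the margin.**

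| Analysed | L | Result |
|---|---|---|
| 166/230, one documented failure left out | 66.04% | pass |
| 166/231, that failure restored | 65.73% | fail |
| 166/230, one documented failure counted as patent | 66.04% | pass |
| 165/230, that subject counted as failed | 65.59% | fail |

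**5. Away from the margin.** 167/230 gives 66.50% and 167/231 gives 66.18%, so both pass. At about the planned rate, 173/230 gives 69.2%. Restoring seven failures gives 173/237 and 67.0%, still a pass.

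**6. Type I error for assumed counts.** Take 230 subjects with true patency of exactly 66%. The counts are assumptions; the SAP gives none.
- Documented failures left out: one changes nothing, because 229 subjects still need 166 patent. With 2, 3 or 5 left out the required counts are 165/228, 164/227 and 163/225, and type I error is 3.7%, 5.0% and 6.7%.
- Documented failures counted as patent: 1, 2 or 5 give 3.7%, 5.0% and 11.2%.

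**7. Month 24 patency and fracture.** No reversal, re-imaging or new-loss rates are in the SAP, so no effect size follows from it.

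**The case against.** **The definition is already cumulative.** It leans that way, as do the success criterion, the event-free approach in SAP 9.2.8 and the Kaplan-Meier figure of primary patency listed in SAP 14. But 9.4.2 is the section that decides who is analysed, and its routes do not carry the definition through. The figure has no stated event or censoring rule and does not govern the tabulated rate.

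**Redacted text may settle it.** Text after the definition in 6.2.2 is blacked out, and so is a note to the secondary patency item. This is a fair caution, chiefly for Month 24. The visible rule in 9.4.2 still reads as described.

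**The tipping-point analysis covers it.** SAP 9.2.3 plans one for missing data. These failures are known, so classing them as missing is itself the problem.

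**It will be rare.** This largely stands. The scheduled visits are Day 30 and then Month 12. The case needs an unscheduled core-lab image, a loss without CDTLR and no Month 12 image, all in one subject. Nothing in the SAP shows how often such images reach the core lab.

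**Carry-forward has its own bias.** This also stands. Noise near PSVR 2.0 can make a patent stent read as lost, and carry-forward makes that permanent. A rule based on any image must also respect the precedence of angiography over duplex.

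**Stronger readings to avoid.** A reader might infer that the SAP prescribes visit-by-visit reading of patency and fracture. It does not; for the later time points it is silent, and the sentence in 9.5 about serial measures takes ABI as its example. A reader might also infer that a fracture could revert to success. That is not realistic; the plausible route is that a fractured stent leaves the count when a later X-ray is missing.

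**Conclusion.** The point holds for the primary endpoint. Read literally, SAP 9.4.2 leaves out, or can count as patent, a subject with a documented pre-window loss, and this conflicts with 6.2.2 and the success criterion in 9.1. The error runs only in the device's favour. The number affected is unknown and likely small. One subject decides the result only at the pass mark (66.04% against 65.73%); at the planned rate even seven do not. The type I error figures rest on assumed counts and a true rate of exactly 66%. The documents therefore show a rule that can bias the primary result, not that the result is biased.

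The Month 24 and fracture part is secondary: a missing rule for descriptive rates that have no performance goal, with an effect that the SAP does not allow one to size.

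**What to change.** **SAP 9.4.2.** State that any core-lab-read loss of patency after the index procedure and through the 12-month assessment counts as a failure and keeps the subject in the denominator, with or without a 12-month image. Angiography takes precedence over duplex from the same assessment. Limit the later-patent rule to subjects with no earlier documented loss.

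**SAP 6.2.3, 9.5 and 9.5.1.** Apply the same rule to Month 24 patency, at the PSVR threshold being analysed, and to fracture at Months 24 and 36: a documented loss or fracture stays a failure in the denominator at every later time point, and the rates are reported as cumulative.

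**SAP 14.** Give the Kaplan-Meier patency figure event and censoring rules that match.

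**Cost.** Wording and derivation code; the 12-month part can use only unscheduled images that the core lab has read. Rates may be slightly less favourable, and a single false-positive duplex reading is not undone by a later duplex reading.

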## 7. DATA QUALITY ASSURANCE AND COMPUTING ENVIRONMENT

The Investigators are responsible for signing the Investigator Agreement prior to the commencement of the study and for ensuring that this trial is conducted according to this study Protocol, GCPs, Declaration of Helsinki, 21 CFR Parts 50, 54, 56 and 812, ISO 14155:2011 (Section 9) and any other local, national or IRB / EC requirements that apply to Clinical Investigations at their center.

It is also the Investigator's responsibility to ensure that all sub-investigators and staff assisting with this study have the appropriate qualifications and that they complete training on the Protocol, investigational devices and study procedures, and that subject confidentiality is respected.

Standardized electronic case report forms (eCRFs) will be used to collect complete and accurate records of the clinical data from the MIMICS-2 trial according to the GCP requirements. The Investigator and/or study staff under his/her direction is responsible for accurately recording the clinical data for this study and submitting it to the Sponsor in a timely manner.

Statistical analyses will be performed using the SAS Software package .

## 8. PATIENT POPULATIONS

### 8.1. Analysis Populations

- *Intention-to-Treat (ITT) Analysis Set*: includes all enrolled subjects.
- *Modified Intention-to-Treat (mITT) Analysis Set*: includes all enrolled subjects in whom the BioMimics 3D Stent is implanted. Those subjects in whom the procedure is aborted without deployment (implantation) of a stent are excluded in this analysis set. This is the primary analysis set for the primary safety and effectiveness endpoints, as well as secondary and exploratory endpoints. If no subjects are excluded, that is, if the ITT and mITT analysis sets contain the same subjects, then all mITT analyses will revert to the ITT analysis set and the mITT analysis set will be eliminated.

- *Per Protocol (PP) Analysis Set*: includes all mITT subjects who additionally met all inclusion/exclusion criteria. This is a secondary analysis set for the primary safety and effectiveness endpoints, as well as secondary endpoints.

While mITT is intended as the primary analysis set for all safety and effectiveness endpoints, the primary safety and effectiveness endpoints will additionally be evaluated in the ITT and PP analysis sets as supportive information. All subjects excluded from mITT and PP analysis sets will be described in the final study report and the reasons detailed. If the ITT and mITT analysis sets contain the same subjects, then all mITT analyses will revert to the ITT analysis set and the mITT analysis set will be eliminated.

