## 6. INVESTIGATIONAL PLAN

### 6.1. Overall Study Design and Plan

The MIMICS-2 Study is a prospective, single arm, multicenter trial to demonstrate the safety and effectiveness of Veryan's BioMimics 3D Stent System. The BioMimics 3D self-expanding Nitinol stent is intended to improve luminal diameter in the treatment of symptomatic de-novo obstructive or occlusive lesions in native femoropopliteal arteries with reference vessel diameters ranging from 4.0 – 6.0 mm. Safety and effectiveness outcomes in the MIMICS-2 study will be compared to established performance goals defined by VIVA Physicians, Inc. for the clinical evaluation of safety and effectiveness of Nitinol stents used in the treatment of symptomatic disease of the femoropopliteal artery.

A total of 280 subjects will be enrolled into the MIMICS-2 Study to provide 230 subjects for evaluation at 12 months. This study will be conducted in up to 40 centers in the US and up to 13 centers in Europe and Japan. Up to 40% of total study population may be enrolled outside the US. A minimum of 30 evaluable subjects is required in Japan for the 12 month assessment time point. No site may enroll more than 35 subjects.

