### 9.4. Primary Endpoint Analysis

Endpoints will be analyzed using the modified intention-to-treat analysis set as described below. The study will be considered successful if both primary safety and efficacy endpoints have been met. An additional supportive analysis will be conducted in the ITT analysis set for the primary safety and effectiveness endpoints.

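### Secondary safety endpoints 1 to 3, including Month-12 MAE and SAEs to Month 36, are planned only in subjects with a stent implanted, with no all-enrolled counterpart

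*SAP*

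**What the plan says.** SAP Section 8.1 defines the mITT set as one that "includes all enrolled subjects in whom the BioMimics 3D Stent is implanted". It adds: "Those subjects in whom the procedure is aborted without deployment (implantation) of a stent are excluded in this analysis set". On its use, the section says: "This is the primary analysis set for the primary safety and effectiveness endpoints, as well as secondary and exploratory endpoints".

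The same section then states: "While mITT is intended as the primary analysis set for all safety and effectiveness endpoints, the primary safety and effectiveness endpoints will additionally be evaluated". The sentence goes on to name ITT and PP as the supportive sets. Section 9.4 repeats the ITT part: "An additional supportive analysis will be conducted in the ITT analysis set for the primary safety and effectiveness endpoints". Section 9.2.3 places the tipping-point analysis of the primary endpoints on ITT.

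For the secondary endpoints, Section 9.5 says: "The mITT analysis set will be used for these analyses". Three of them concern safety: the individual 30-day MAE components (1), Month-12 MAE with its components (2), and the third, worded as "Overall rate and incidence of type of serious adverse events from Day 0 through completion of Study follow-up at Month 36".

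Section 6.1 gives the purpose of the trial as "to demonstrate the safety and effectiveness of Veryan's BioMimics 3D Stent System".

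Section 8.1 also says that mITT analyses revert to ITT if the two sets are identical, and that subjects left out of mITT will be described with reasons.

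**The concern.** Membership of mITT depends on something that happens after enrolment, namely that a stent was implanted. That is reasonable for patency and stent fracture, which cannot be assessed without a stent. It is a poor basis for safety rates. What is being evaluated is a stent with its delivery system, and harm during a failed delivery belongs to the safety of that system.

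Take an enrolled subject whose procedure is abandoned without implantation and who then has an SAE, a major amputation or a death. That subject is outside the results for secondary endpoints 1 to 3. These endpoints are tabulated without a performance goal, so the reported rate is the whole result and the choice of denominator decides what it describes. As planned, the rates describe safety given successful implantation.

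**Working it through.** **1. Which analyses include a subject without an implant**

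| Result | Set named in the SAP | Non-implanted subject included? |
|---|---|---|
| Primary 30-day MAE | mITT; ITT and PP supportive (8.1, 9.4); tipping point on ITT (9.2.3) | Yes, in ITT |
| Secondary 1: 30-day MAE components | mITT (8.1, 9.5); PP secondary (8.1) | No |
| Secondary 2: Month-12 MAE and components | mITT; PP secondary | No |
| Secondary 3: SAEs, Day 0 to Month 36 | mITT; PP secondary | No |
| AE/SAE and device-failure summaries (9.7.1, 9.7.2); Tables 6.1-6.3, 9.0-9.6 | None named | Not determined |

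PP is drawn from mITT, so it does not bring these subjects back. The table list does name a set in some places: Table 8 is labelled mITT and Table 15.a ITT. The AE tables carry no such label.

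**2. The primary safety endpoint**

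The plan's own figure comes first. With the one-sided 97.5% Agresti-Coull lower limit against 88% and a true event-free rate of 98%, the success rule is at least 213 event-free of 230, or at least 250 of 271. Exact binomial power exceeds 0.9999 at either size, in line with the stated figure of over 99% (Section 9.1).

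Next, take 271 enrolled subjects (Section 9.1). Assume 5 MAEs among the implanted, which is about 2%, and k non-implanted subjects who all have an MAE. The ITT limits are:

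- k = 3: 8 MAEs of 271, lower limit 94.2%
- k = 5: 10 of 271, lower limit 93.3%
- k = 8: 13 of 271, lower limit 91.9%

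The limit stays above 88% up to 21 MAEs of 271 (88.4%). The 30-day conclusion is therefore not in question.

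**3. Month-12 MAE**

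The SAP gives neither a count of non-implanted subjects nor an expected Month-12 rate. Assumptions: 3, 5 or 8 of 271 not implanted; 1, 2 or 3 events among them; about 10% MAE among the implanted. Relative understatement = 1 − (mITT rate ÷ ITT rate).

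| Not implanted | Events among them | mITT | ITT | Relative understatement |
|---|---|---|---|---|
| 3 | 1 | 27/268 = 10.07% | 28/271 = 10.33% | 2.5% |
| 5 | 2 | 27/266 = 10.15% | 29/271 = 10.70% | 5.1% |
| 8 | 3 | 26/263 = 9.89% | 29/271 = 10.70% | 7.6% |

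The worst case, in which every non-implanted subject has an event, gives:

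- Base of about 10%: ITT rates of 30/271 = 11.1%, 32/271 = 11.8% and 34/271 = 12.5%.
- Base of about 5% (13 events among the implanted): mITT rates of 13/268 = 4.9%, 13/266 = 4.9% and 13/263 = 4.9%, against ITT rates of 16/271 = 5.9%, 18/271 = 6.6% and 21/271 = 7.7%.

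The gap is about 1 to 3 percentage points on either base.

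In the opposite case, 8 non-implanted subjects have no events. Then mITT gives 26/263 = 9.89% and ITT 26/271 = 9.59%, so mITT is slightly the less favourable of the two.

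**The case against.** The strongest reply is that the plan already looks at all enrolled subjects where failed delivery is most likely to do harm. Death, major amputation and clinically driven TLR through 30 days are analysed in ITT and stress-tested in ITT. A reader who stops partway through the key sentence in Section 8.1 might infer that all safety is confined to implanted subjects. The rest of that sentence, with Sections 9.4 and 9.2.3, rules this out for the primary endpoint. This part of the reply stands.

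A reader might also infer that SAEs and device failures in non-implanted subjects disappear from the report altogether. The SAP does not support that either. Section 9.7.1 speaks of all collected adverse events without a set, Table 6.1 is headed as covering all adjudicated events, and the listings carry no mITT restriction. The opposite is not secured, however. Section 8.1 calls mITT the intended primary set for every safety endpoint, and a programmer could apply it to Section 9.7.

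Third, size and direction are not known. If every enrolled subject received a stent, mITT reverts to ITT and nothing changes. If the non-implanted subjects had no events, mITT looks marginally worse. If they leave the study early, there may be little Month-12 data to add; their follow-up is a matter for the protocol, which is not at hand. All of this limits the size of the point. It does not supply the missing analysis, and a promise to describe excluded subjects with reasons is not a promise to report their outcomes.

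Finally, no success decision rests on secondary endpoints. That is true, and it is why this is an inexpensive improvement and not a threat to the trial's conclusion.

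**Conclusion.** The point holds for secondary endpoints 1 to 3. They are assigned to a set selected on successful implantation, with no ITT counterpart, so events after failed delivery are left out of those results. It does not hold for the primary 30-day MAE endpoint. For Section 9.7 and Tables 6.1-6.3 and 9.0-9.6, the defect is that no set is named; exclusion there is not shown.

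The size is unknown and may be nil. Under the stated assumptions (about 10% Month-12 MAE, 3 to 8 of 271 not implanted, 1 to 3 events among them), the relative understatement is about 2% to 8%. The worst case is about 1 to 3 percentage points.

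A reader might infer a much larger distortion by starting from a 30-day event rate. With 5 MAEs among the implanted, 5/268 against 6/271 is a 16% relative understatement and 5/263 against 8/271 is 36%. That arithmetic is right, but its base rate belongs to the 30-day composite, which already has an ITT analysis. It should not be carried over to Month 12, where events have had longer to accumulate.

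**What to change.** - In Sections 8.1 and 9.5, state that secondary endpoints 1 to 3 are reported in the ITT set, beside or in place of mITT. ITT contains all enrolled subjects and so every subject in whom delivery was attempted. A further population is not needed.
- In Sections 9.7.1 and 9.7.2, and in the titles of Tables 6.1-6.3, 9.0-9.6 and 10, state that AE, SAE, adjudicated-event and device-failure summaries use all enrolled subjects.
- Keep mITT for patency and stent integrity.

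The cost is a few sentences, revised table titles and some additional columns, using data already collected. There are two drawbacks: safety rates may look slightly less favourable, and non-implanted subjects may have shorter follow-up. Showing the number with known status at each time point deals with the second.
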